9.3 POPULATIONS FOR ANALYSES

All randomized participants will be included in the dataset (ITT).

9.4 STATISTICAL ANALYSES

9.4.1 GENERAL APPROACH

Checks of assumptions underlying statistical procedures will be performed and all corrective procedures will be applied as necessary.

9.4.2 ANALYSIS OF THE PRIMARY EFFICACY ENDPOINT(S)

Statistical Analyses: Data for Aim 1 are repeated-measures data and will not support bivariate analysis by Pearson and/or Spearman correlations, as autocorrelation can cause transient or spurious relationships with high correlations for some periods and none for others. Similarly, for a linear regression model, this type of data may cause residuals for the same individual to be correlated. Therefore, we will employ linear mixed models featuring fixed effects and random effects (i.e. random intercepts) to account for within subject variation. We will also perform a differences-in-differences analysis comparing change between baseline and the end of the intervention to determine which strategy resulted in greater improvement in PF.

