9.4.4 ACCOMODATING ADDITION OF TENS UNIT TO THE CONTROL ARM

An ITT analysis "Includes all randomized patients in the groups to which they were randomly assigned, regardless of their adherence with the entry criteria, regardless of the treatment they actually received, and regardless of subsequent withdrawal from treatment or deviation from the protocol."^{ref} Accordingly, we will follow the original analysis plan described above with regard to analyzing results by study-arm. In addition to the ITT analysis, however, we will conduct a sensitivity analysis by repeating the statistical procedures in a per-protocol fashion wherein the members of the control arm who did not receive a TENS unit will be dropped from the sample. Directions, magnitudes, and significance of treatment effects will be presented for both analyses.

Furthermore, because the TENS unit will appear in both study arms - and unevenly in the control arm – we recognize that an ITT analysis strictly *by* study-arm risks misidentifying the effect of treatment, while a per-protocol analysis risks introduction of bias. Therefore, we will conduct an additional linear mixed model regression analysis using a term for the TENS that captures the effect of the TENS separately from the effects of study-arm assignment. The model used to fit these data is as follows:

 $\hat{y}_{it} = \beta_0 + \beta_1 time_{it} + \beta_2 study_arm_{it} + \beta_3 TENS_{it} + e_{it}$

where time represents change in time from baseline, study_arm indicates status as a control or experimental participant (0= control and 1=experimental), *i* is the individual participant, and TENS indicates TENS unit usage (0= no TENS unit and 1=TENS unit). We can therefore write a regression equation describing each type of patient differentiated by the addition of the TENS unit to control conditions:

Treatment: $\hat{y}_{it} = \beta_0 + \beta_1 time_{it} + \beta_2 study_arm_{it} + \beta_3 TENS_{it} + e_{it}$

Control w/o TENS: $\hat{y}_{it} = \beta_0 + \beta_1 time_{it} + e_{it}$

Control w/ TENS:

 $\hat{y}_{it} = \beta_0 + \beta_1 time_{it} + \beta_3 TENS_{it} + e_{it}$

In this manner we isolate the term of interest (study_arm). Given we are only adding one term but 20 subjects, we are comfortable relying on the original power calculation.

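### The primary mixed model has random intercepts only, so standard errors for change-over-time terms may be too small if weekly scores are serially correlated or individual slopes differ

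*Combined protocol and SAP*

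**What the plan says.** Section 9.4.2 of the combined protocol and SAP rules out simple correlations because "autocorrelation can cause transient or spurious relationships". It adds that, in a linear regression, "this type of data may cause residuals for the same individual to be correlated". Its answer is linear mixed models with "random effects (i.e. random intercepts) to account for within subject variation". No random slope, residual covariance structure or robust standard error is named anywhere. A second analysis follows: "We will also perform a differences-in-differences analysis comparing change between baseline and the end of the intervention". How its standard error is obtained is not stated.

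Section 9.4.1 makes a general promise: "Checks of assumptions underlying statistical procedures will be performed and all corrective procedures will be applied as necessary".

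Section 9.4.4 announces an "additional linear mixed model regression analysis using a term for the TENS". The displayed equations contain fixed effects for time, study arm and TENS plus an error term. They show no person-level random term and no arm-by-time term, and the text names study arm as the term of interest.

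The Schedule of Activities (section 1.3) gives ten PROMIS time points: Days 1, 7, 14, 21, 28, 35, 42, 49, 56 and 60. Sections 3 and 9.1 frame the primary endpoint as physical function over time, compared between arms.

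**The concern.** A random intercept removes stable differences between people. What remains is treated as independent noise, so Day 1 and Day 7 are taken to be as closely related as Day 1 and Day 60. Scores taken close together may be more alike than that, and people may recover at different rates. In either case the model credits the data with more information about change than they hold. Confidence intervals for time and arm-by-time terms are then too narrow, and so is the interval for an end-minus-baseline contrast read from this model. These are the terms that speak to a question about function over time.

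A smaller point concerns section 9.4.4. Its equations omit the person-level term that a mixed model needs. An analyst who coded them literally would treat repeated scores from one person as if they came from different people.

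**Working it through.** **Inputs from the documents.** Ten time points (section 1.3), random intercepts only (9.4.2) and a 0.05 level (9.2, taken as two-sided). Arm size cancels from the ratios below.

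**Inputs assumed.** The documents give no intraclass correlation, autocorrelation, slope variance or standard error, so there is no figure of the plan's own to reproduce. I set the total variance to 1 before adding any slope variance, with half of it between persons unless stated. Weekly AR(1) is 0.3, 0.5 or 0.7. Alternatively, the random-slope SD over the whole follow-up is 0.3 to 0.7 score-SD.

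**Formulas.** Let w = (day − 1)/7, running from 0 to 8.43 weeks with mean 4.33. Let x = w − mean, so Sxx = Σx² = 77.55. Let V be the true 10 × 10 within-person covariance matrix and C the centring matrix.

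- Residual variance that the random-intercept model estimates: s² = trace(CVC)/9.
- Slope: model variance s²/Sxx, true variance x′Vx/Sxx². The true-to-model SE ratio is R = √[(x′Vx/Sxx)/s²].
- Last-minus-first contrast: model variance 2s², true variance c′Vc, so R = √[c′Vc/(2s²)].
- Actual type I error = 2Φ(−1.96/R).

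**Worked example, AR(1) 0.5.** s² = 0.4061 and x′Vx/Sxx = 1.0184, so R = √(1.0184/0.4061) = 1.58 and the error rate is 2Φ(−1.24) = 22%. For the contrast, c′Vc = 0.9971 and 2s² = 0.8122, so R = 1.11 and the error rate is 8%.

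| True structure | Arm-by-time: R | Type I | Contrast: R | Type I |
|---|---|---|---|---|
| Equal correlation | 1.00 | 5% | 1.00 | 5% |
| Intercept + AR(1) 0.3 | 1.34 | 14% | 1.05 | 6% |
| Intercept + AR(1) 0.5 | 1.58 | 22% | 1.11 | 8% |
| Intercept + AR(1) 0.7 | 1.87 | 30% | 1.22 | 11% |
| Random slope SD 0.3 | 1.08 | 7% | 1.03 | 6% |
| Random slope SD 0.5 | 1.21 | 10% | 1.09 | 7% |
| Random slope SD 0.7 | 1.36 | 15% | 1.15 | 9% |

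The AR(1) rows do not depend on the between-person share, because the intercept cancels. The random-slope rows do: at a share of 0.7, slope SDs of 0.3 and 0.7 give 8% and 20% for arm-by-time, and 6% and 11% for the contrast.

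**Simulation check.** I used 120 trials per scenario, 75 per arm, 25% random withdrawal and a between-person share of 0.7. Random-intercept fits rejected arm-by-time in 5% (equal correlation), 20% (AR(1) 0.5) and 12% (slope SD 0.5) of trials. The Monte Carlo standard error is about 2 points at 5% and 4 points at 20%.

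**What is not affected.** For the averaged arm effect with a random intercept, the simulated model-to-true SE ratio was about 1.04 in all three scenarios. Rejection was 7% to 8%, within simulation error of 5%. A two-sample comparison of each person's own change estimates c′Vc directly, so it does not rely on the random-intercept assumption.

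**Section 9.4.4 taken literally.** With no person-level term, the variance of the study-arm effect is understated by 1 + 9 × ICC. That is 5.5 at ICC 0.5 and 7.3 at ICC 0.7. The SE ratios are √5.5 = 2.35 and √7.3 = 2.70, and the type I errors are 40% and 47%. Simulation at ICC near 0.7 gave 41% to 43%.

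**The case against.** The best defence is that no arm-by-time term is written anywhere. The one treatment term displayed is the study-arm main effect, and with a random intercept its test is sound. The baseline-to-end comparison has its own planned analysis, which is safe if done on per-person changes. A random-intercept model is a legitimate choice, and section 9.4.1 allows corrections. All of this stands, and it limits the point to terms for change over time. It does not remove the point. The stated question is about function over time, and the treatment contrast that answers it is unspecified. Section 9.4.1 names no covariance check, criterion or fallback, which in an unblinded trial (section 6.2) leaves the choice open until results are visible.

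Three stronger readings are tempting and not supported:

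- *The standard errors will be too small.* Under equal correlation they are correct, and the documents contain nothing that settles the correlation pattern.
- *The plan itself says that the scores are autocorrelated.* It says only that autocorrelation can mislead simple correlations and that residuals may be correlated in a linear regression. The mixed model is offered as the remedy.
- *Section 9.4.4 will be fitted as ordinary regression.* Its text says "we will conduct an additional linear mixed model regression analysis using a term for the TENS", and section 9.4.2 defines such models as having random intercepts. The missing term is most plausibly a gap in notation, and the analysis is additional to the ITT analysis.

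**Conclusion.** The concern holds in conditional form. Random intercepts alone do not model the autocorrelation that section 9.4.2 raises. If scores are serially correlated or slopes differ, standard errors for time and arm-by-time terms may be too small. On assumed inputs, arm-by-time type I error runs from 5% (equal correlation) to about 30% (AR(1) 0.7). With half the variance between persons, differing slopes alone give about 7% to 15%. An end-minus-baseline contrast read from the same model runs from 5% to 11%. The averaged arm effect with a random intercept and a per-person change-score analysis are not affected. The 40% to 47% figure for section 9.4.4 applies only if its equations were fitted exactly as displayed. This is a cheap improvement to the specification. The documents do not show that the primary analysis is wrong as written.

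**What to change.** 1. In section 9.4.2, state the arm-by-time or arm-by-visit contrast that answers the primary question. This settles what is estimated as well as its standard error, so it should be decided deliberately.
2. Pre-specify the covariance: visit as a factor, arm-by-visit terms, unstructured within-person covariance and Kenward–Roger degrees of freedom.
3. Name a fallback and its trigger (non-convergence): a random slope, or a random intercept plus AR(1), with cluster-robust standard errors. The gaps between time points are unequal (6 days at the start, 4 at the end), so base the AR(1) on actual days.
4. State that the baseline-to-end comparison uses per-person changes, if that is the intention.
5. Add the person-level intercept u_i to every equation in section 9.4.4, so that they match the text's description of a mixed model.

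The cost is SAP wording and standard software options, with no new data and no change to conduct. The downside is more parameters: ten time points need 10 × 11/2 = 55 variances and covariances, with 25% withdrawal assumed in section 9.2. Non-convergence is therefore possible, which is why the fallback must be written in advance.

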9 STATISTICAL CONSIDERATIONS

9.1 STATISTICAL HYPOTHESES

• Primary Efficacy Endpoint(s):

Primary Outcome: Physical function over time as measured by PROMIS PF score (T- Scored, Continuous)

Question: Which intervention is more effective in improving physical function?

Independent variable of interest: Comparator received, intervention vs. control (Dichotomous)

Potential Covariates: Age, gender, race, ethnicity, mental health comorbidities, chronic pain diagnosis, use of other pain medications (neuropathic pain medications, NSAIDS, antidepressants), benzodiazepine use, number of office visits during study period, baseline PROMIS[®] scores, encounter month, physician years of practice, physician gender.

• Secondary Efficacy Endpoint(s):

Secondary Outcome: Pain over time as measured by PROMIS Pain Interference Score (T-Scored, Continuous)

Question: Which intervention is more effective in improving patient's pain interference?

Independent variable of interest: Comparator received, intervention vs. control (Dichotomous).

Potential Covariates: Same as Primary Aim.

Secondary Outcome: Effects of lower back pain symptom severity on work productivity and regular activities over time as measured by WPAI:LB (T-Scored, Continuous).

Question: Which intervention is more effective in improving patient's work productivity and participation in regular activities?

Independent variable of interest: Comparator received, intervention vs. control (Dichotomous).

Potential Covariates: Same as Primary Aim.

Secondary Outcome: New Opioid Prescription over 90MME (Dichotomous)

Question: Which intervention is more effective in reducing opioid prescriptions of 90 Morphine Milligram Equivalents (MME) or greater?

Independent variable of interest: Comparator received, intervention vs. control (Dichotomous).

Potential Covariates: Same as Primary Aim.

Statistical Analyses: As in the primary aim analyses, we will employ mixed effects models featuring both fixed effects and random effects to account for within subject variation.

Because this particular outcome is binary, we will use mixed logistic regressions in which the log odds of the outcomes are modeled as a linear combination of the predictors.

Secondary Outcome: Satisfaction with Pain Treatment and Healthcare Scores

Question: Which intervention is more effective in improving how satisfied patients feel with their care?

Dependent variable: Pain Treatment and Patient Satisfaction Scores

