9.4.3 ANALYSIS OF THE SECONDARY ENDPOINT(S)

Statistical Analyses: As in the primary aim analyses, we will employ linear mixed models featuring fixed effects and random effects to account for within subject variation. We will also perform a differences-indifferences analysis comparing change between baseline and the end of the intervention to determine which strategy resulted in greater improvement in PF.

Statistical Analyses: As in the primary aim analyses, we will employ linear mixed models featuring fixed effects and random effects to account for within subject variation. We will also perform a differences-indifferences analysis comparing change between baseline and the end of the intervention to determine which strategy resulted in greater improvement in PF. Statistical Analyses: In addition to unadjusted comparisons, we will employ multiple linear regression models.

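### The primary endpoint has two unranked analyses, and the mixed model's fixed effects, treatment contrast and handling of baseline physical function are not settled

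*Combined protocol and SAP*

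**What the plan says.** Section 9.4.2 explains why repeated measures rule out simple correlation and regression, and concludes that "we will employ linear mixed models featuring fixed effects and random effects (i.e. random intercepts) to account for within subject variation". It lists no fixed effects. It then adds the baseline-to-end difference-in-differences: "We will also perform a differences-in-differences analysis comparing change between baseline and the end of the intervention to determine which strategy" did better. Its stated purpose is "to determine which strategy resulted in greater improvement in PF". That nearly restates the primary question in section 9.1: "Question: Which intervention is more effective in improving physical function".

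Two other sections bear on the model.

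- Section 9.1 names trial arm as the variable of interest. It gives a list of potential covariates, with no selection rule, that ends "number of office visits during study period, baseline PROMIS[®] scores, encounter month, physician years of practice, physician gender".
- Section 9.4.4 writes out an additional model with time from baseline, study arm and TENS as main effects. It calls study arm the term of interest and says that only one term has been added. This implies a base model of time plus study arm, with no baseline PF and no arm-by-time term.

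The pair of methods is carried further. Section 9.4.3 opens "As in the primary aim analyses, we will employ linear mixed models featuring fixed effects and random effects to account for within subject variation" and repeats the difference-in-differences. Section 9.4.4 says of the intention-to-treat analysis that "we will follow the original analysis plan described above with regard to analyzing results by study-arm", and adds a sensitivity analysis "repeating the statistical procedures in a per-protocol fashion". The populations are therefore ranked, but the two methods are not.

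**The concern.** Sections 3 and 4.1 define the primary outcome as change in PF. The difference-in-differences targets change from Day 1 to Day 60. A study-arm main effect without arm by time targets a gap averaged over visits. If that is the mixed model, the two analyses estimate different quantities, one can be significant when the other is not, and the plan has no rule for that case.

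Handling of baseline adds to this. PF could be a covariate (section 9.1, only as a possibility), the time-zero outcome row (suggested by time from baseline in section 9.4.4, not stated), or subtracted (the difference-in-differences). If Day 1 is an outcome row under a main-effects model, the arm term averages in a pre-treatment visit, absorbs part of any chance baseline gap, and does not test change. The trial is unblinded (section 6.2), so it is safer to fix the deciding analysis before outcomes are summarised by arm.

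**Working it through.** The plan gives no figure for this point. From the documents: ten PF assessments on Days 1, 7, 14, 21, 28, 35, 42, 49, 56 and 60 (section 1.3); an effect of 0.6 SD, not tied to any visit or contrast (section 9.2); an SD of 10 points and an MCID of 2 points (section 8.1). Arms are 75 vs 75, or 75 vs 99 for intention to treat because the 24 earlier controls stay in (sections 6.2, 9.3, 9.4.4). The low bound is 56 per arm, from 75 × 0.75 = 56.25 with the plan's 25% withdrawal.

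Assumed: within-person correlation ρ from 0.5 to 0.8, compound symmetry, complete data, two-sided 0.05, normal approximation, the same effect against both kinds of control, and the shape of the effect over time.

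**Variances.** Let f = 1/n₁ + 1/n₂, in SD units.

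- Arm main effect with Day 1 as an outcome row: f(1 + 9ρ)/10.
- Difference-in-differences: 2f(1 − ρ).
- The covariance of these two is zero, so the tests are independent.

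**Type I error if either test could count.** This does not depend on effect shape or sample size.

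- Day 1 as outcome row: 1 − 0.95² = 9.75%.
- Baseline as covariate, nine-visit average: correlation with the difference-in-differences is √((1 + 9ρ)/18) = 0.553 to 0.675, giving 8.9% to 8.5%.
- Arm-by-time slope: correlation 0.677, giving 8.5%.

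**Linear growth to 0.6 SD at Day 60, Day 1 as outcome row, main effects only.** The mean share of the effect over ten visits is (0+6+13+20+27+34+41+48+55+59)/(59 × 10) = 303/590 = 0.514, so the arm term estimates 0.6 × 0.514 = 0.308 SD. Example with 56 per arm and ρ = 0.5: the arm-term SE is √(2/56 × 0.55) = 0.140, and power is Φ(0.308/0.140 − 1.96) = 0.594. The difference-in-differences SE is √(2/56) = 0.189, with power 0.888. Disagreement is 0.594 × 0.112 + 0.406 × 0.888 = 0.427.

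| Arms | ρ | Power, arm term | Power, difference-in-differences | Disagree |
|---|---|---|---|---|
| 56 vs 56 | 0.5 | 0.594 | 0.888 | 0.427 |
| 56 vs 56 | 0.8 | 0.437 | 0.999 | 0.563 |
| 75 vs 75 | 0.5 | 0.721 | 0.957 | 0.299 |
| 75 vs 75 | 0.8 | 0.549 | >0.999 | 0.451 |
| 75 vs 99 | 0.5 | 0.775 | 0.975 | 0.239 |
| 75 vs 99 | 0.8 | 0.604 | >0.999 | 0.396 |

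**Other readings, same ranges.**

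- Baseline as covariate: disagreement is 0% to 11% for a full effect from Day 7 or a ramp complete by Day 28, and 0% to 13% for linear growth. It is 13% to 63% for an effect that halves by Day 60.
- Mixed model testing arm by time: 0% to 11% for linear growth, but 1% to 32% for a full effect from Day 7.

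**Baseline gap.** The SE of the Day 1 difference is 10√f: 1.89 points (56 vs 56), 1.63 (75 vs 75), 1.53 (75 vs 99). A gap of at least 2 points has probability 29%, 22% and 19%. With Day 1 as an outcome row the arm term carries (1 + 9ρ)/10 = 55% to 82% of it, so a 2-point gap moves the arm term by 1.1 to 1.6 points. It moves the difference-in-differences by 2(ρ − 1) = −1.0 to −0.4 points, in the opposite direction.

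**The case against.** The plan can be read more kindly, and part of that reading stands. Section 9.4.2 reasons its way to the mixed model and only then adds the second method. The opioid analysis in section 9.1 likens itself to the primary analyses and names only mixed models, and the added analysis in section 9.4.4 is again a mixed model. The mixed model therefore probably leads, but no section says so.

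Four stronger inferences are not supported.

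- That the plan is silent on fixed effects and baseline. Sections 9.1 and 9.4.4 both bear on them; the defect is that they disagree and neither settles the primary model.
- That the primary model will omit arm by time. The equation in section 9.4.4 belongs to an additional analysis and may be schematic. With arm by time tested, the large disagreement under linear growth disappears.
- That success on either test is the planned rule. The documents state no such rule; the type I error figure shows what an unranked pair would permit.
- That the trial may stop early on an undefined result. Section 10.1.2 includes reaching the primary endpoint in a generic list of possible grounds for closure, but no interim analysis is described. Likewise, section 6.2 explains the lack of blinding by participants' awareness and does not say that outcomes are reviewed by arm.

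**Conclusion.** The point holds in this form: two analyses of the primary endpoint, none named as decisive, and a mixed model whose terms, contrast and use of baseline PF are left open between sections that do not agree. The firmest consequence is the type I error of about 8.5% to 9.75% if either test could count, which needs no assumption about effect shape. The power of 44% to 78% and the disagreement of about 24% to 56% are conditional on linear growth, Day 1 as an outcome row, no arm-by-time term and ρ of 0.5 to 0.8. They illustrate one plausible reading and do not forecast the trial. For an early sustained effect with baseline as a covariate the conflict is small. This should be fixed before outcomes are summarised by arm.

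**What to change.** In section 9.4.2, name one deciding analysis: a linear mixed model with arm, visit, arm by visit and adjustment for baseline PF, and one prespecified arm contrast. The Day 60 difference matches the plan's own baseline-to-end comparison. The baseline-adjusted average over post-baseline visits is an acceptable alternative if the sponsor chooses it before outcomes are summarised by arm. To keep every randomised participant, as section 9.3 requires, Day 1 may instead stay as an outcome row with the arms constrained to a common baseline mean.

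Label the difference-in-differences supportive. Reconcile sections 9.1, 9.4.2 and 9.4.4, and use the same baseline handling and arm-by-time term in the section 9.4.4 model and for Pain Interference.

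The cost is SAP wording and a few more parameters; baseline and weekly PF are already collected. A Day 60 contrast leans more on exit surveys, which matters given the withdrawals for low survey compliance noted in the summary of changes. The average gives less credit to a late effect. A model fitted only to post-baseline rows drops anyone with no post-baseline survey, which the common-baseline form avoids.
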